- 614 responsibilities to ensure a sufficient number of subjects are enrolled;
- 615 7) Ensure that subjects signed the informed consent forms prior to study initiation,
616 and ensure their safety;
- 617 8) If serious adverse events occur, investigators must immediately take appropriate
618 therapeutic measures for the subjects, and report the events to the Ethics Committee,
619 the sponsor, and the State Food and Drug Administration within 24h after informed of
620 these events. Meanwhile, investigators should ensure the subjects receive appropriate
621 treatment in case of adverse events;
- 622 9) Ensure that the data is true, accurate, complete, timely, and legally recorded in the
623 medical files and CRF;
- 624 10) Accept the monitoring and auditing of the monitors as well as inspecting of drug
625 supervision and management department so as to ensure the quality of the clinical
626 study;
- 627 11) Ensure no conflict exists with other clinical studies;
- 628 12) The interests of the subjects are priority in any situation. Protecting subjects from
629 adverse events is consistent with the protocol, but any AEs and deviations from the
630 protocol should be described in the final report;
- 631 13) Any modification (for subjects' safety) that deviate from the protocol should be
632 reported to the Ethics Committee and the sponsor;
- 633 14) If unexpected events occur, investigators should terminate the clinical study and
634 notify the subjects and their doctors;
- 635 15) Take primary responsibility to ensure the validity, clarity and reliability of all
636 documents relating to the study;
- 637 16) Any modification to the original data must be signed by an authorized person and
638 dated, and the original records must be retained for future reference;
- 639 17) After completion of the follow-up for the study, investigators should submit a
640 final study report to the sponsor;
- 641 18) They also should maintain confidentiality obligations regarding information
642 provided by the sponsor during the entire process of the study.

643 **17.3 Responsibilities of CRO**

- 644 1) Monitor the entire process of the study;

-
- 645 2) Promptly update any adverse events or deviations to sponsor and investigators;
- 646 3) Follow the protocol and report any variances from the protocol to sponsor in
647 writing;
- 648 4) Use study drugs strictly according to the protocol, and report any deviations to
649 sponsor;
- 650 5) Conduct systematic monitoring for the study in accordance with GCP principles;
- 651 6) Obtain the informed consent of the subjects;
- 652 7) In accordance with national regulations, the case record form should be recorded
653 on time and consistent with the data from the subject;
- 654 8) Record and report any adverse events to sponsor;
- 655 9) Retain records for subjects, as well as any study terminations;
- 656 10) After completion of the follow-up for the study, the CRO should submit a final
657 study report to the sponsor and investigators;
- 658 11) They also should maintain confidentiality obligations regarding information
659 provided by the sponsor during the entire process of the study.
- 660

661 **Appendix 1. Definitions**

662

663 **Death:** Deaths that are not caused by definite non-cardiac factors are deemed as
664 cardiac deaths. Specifically, any unexpected deaths in subject are deemed as cardiac
665 deaths, even if they also have potential fatal non-cardiac diseases (for example, cancer
666 and infection).

667 **Cardiac death:** any deaths without known cause, and deaths caused by immediate
668 heart-related factors (such as MI, low cardiac output heart failure or fatal arrhythmia)
669 are deemed as cardiac deaths, including those related to surgery and accompanied
670 treatment.

671 **Vascular death:** deaths caused by cerebrovascular diseases, pulmonary embolism,
672 aneurysm rupture or other vascular diseases.

673 **Non-vascular death:** any deaths that are not covered in the definitions above,
674 including those caused by infection, pyemia, pulmonary diseases, accident, suicide or
675 injury.

676

677 **Myocardial infarction.** Myocardial infarction is defined according to the third
678 Universal Definition of Myocardial Infarction.

679 **Type 1: Spontaneous myocardial infarction.**

680 Spontaneous myocardial infarction related to atherosclerotic plaque rupture,
681 ulceration, fissuring, erosion, or dissection with resulting intraluminal thrombus in
682 one or more of the coronary arteries leading to decreased myocardial blood flow or
683 distal platelet emboli with ensuing myocyte necrosis. The patient may have
684 underlying severe CAD but on occasion non-obstructive or no CAD.

685 **Type 2: Myocardial infarction secondary to an ischaemic imbalance**

686 In instances of myocardial injury with necrosis where a condition other than CAD
687 contributes to an imbalance between myocardial oxygen supply and/or demand, e.g.
688 coronary endothelial dysfunction, coronary artery spasm, coronary embolism,

689 tachy-/brady-arrhythmias, anaemia, respiratory failure, hypotension, and hypertension
690 with or without LVH.

691 **Type 3: Myocardial infarction resulting in death when biomarker values are**
692 **unavailable**

693 Cardiac death with symptoms suggestive of myocardial ischaemia and presumed new
694 ischaemic ECG modification or new LBBB, but death occurring before blood samples
695 could be obtained, before cardiac biomarker could rise, or in rare cases cardiac
696 biomarkers were not collected.

697 **Type 4a: Myocardial infarction related to percutaneous coronary intervention**
698 **(PCI)**

699 Myocardial infarction associated with PCI is arbitrarily defined by elevation of cTn
700 values $>5 \times$ 99th percentile URL in patients with normal baseline values (\leq 99th
701 percentile URL) or a rise of cTn values $>20\%$ if the baseline values are elevated and
702 are stable or falling. In addition, either (i) symptoms suggestive of myocardial
703 ischaemia, or (ii) new ischaemic ECG modification or new LBBB, or (iii)
704 angiographic loss of patency of a major coronary artery or a side branch or persistent
705 slow- or no-flow or embolization, or (iv) imaging demonstration of new loss of viable
706 myocardium or new regional wall motion abnormality are required.

707 **Type 4b: Myocardial infarction related to stent thrombosis**

708 Myocardial infarction associated with stent thrombosis is detected by coronary
709 angiography or autopsy in the setting of myocardial ischaemia and with a rise and/or
710 fall of cardiac biomarkers values with at least one value above the 99th percentile
711 URL.

712 **Type 5: Myocardial infarction related to coronary artery bypass grafting**
713 **(CABG)**

714 Myocardial infarction associated with CABG is arbitrarily defined by elevation of
715 cardiac biomarker values $>10 \times$ 99th percentile URL in patients with normal baseline
716 cTn values (\leq 99th percentile URL). In addition, either (i) new pathological Q waves

717 or new LBBB, or (ii) angiographic documented new graft or new native coronary
718 artery occlusion, or (iii) imaging evidence of new loss of viable myocardium or new
719 regional wall motion abnormality.

720

721 **Stent thrombosis:** Stent thrombosis is defined according to the definite or probable
722 criteria of the Academic Research Consortium (Circulation 2007;115:2344-51).

723 **1. Definite stent thrombosis**

724 Presence of an acute coronary syndrome with angiographic or autopsy evidence of
725 thrombus or occlusion.

726 **2. Probable stent thrombosis**

727 Unexplained death within 30 days after the procedure, or acute myocardial infarction
728 involving the target-vessel territory without angiographic confirmation.

729 **3. Possible stent thrombosis**

730 All unexplained death occurring at least 30 days after the procedure.

731

732 **Stent thrombosis classification by time frame**

733 **1. Acute stent thrombosis**

734 Occurring within 24 hours after the index PCI.

735 **2. Subacute stent thrombosis**

736 Occurring between 24 hours and 30 days after the index PCI.

737 **3. Late stent thrombosis**

738 Occurring between 31 and 360 days after the index PCI.

739 **4. Very late stent thrombosis**

740 Occurring later than 360 days after the index PCI.

741

742 **Ischemia-driven Target Vessel Revascularization.** Ischemia-driven target vessel
743 revascularization is defined as repeat PCI or bypass surgery of the target lesion(s) and
744 any additional lesions in the main epicardial coronary artery or branches containing
745 the target lesion, with one or more of the following conditions:

- 746 1. Patient had ischemic symptoms and ECG-changes referable to the target lesion.
- 747 2. Diameter stenosis $\geq 50\%$ at follow-up angiography and a positive functional study
748 corresponding to the area served by the target vessel.
- 749 3. Diameter stenosis $< 50\%$ at follow-up angiography but a markedly positive
750 functional study or ECG-modification corresponding to the territory supplied by
751 target vessel.
- 752 4. Diameter stenosis $\geq 70\%$ at follow-up angiography in absence of documented
753 clinical or functional ischemia.

754

755 **Stroke.** Stroke is defined as an acute event of non-hemorrhagic cerebrovascular origin
756 causing focal or global neurologic dysfunction lasting > 24 hours, which is confirmed
757 by both clinical and radiographic criteria.

758

759 **Bleeding.** Bleeding is defined according to the Bleeding Academic Research
760 Consortium (Circulation 2011;123:2736-47).

761 Type 0: no bleeding.

762 Type 1: bleeding that is not actionable and does not cause the patient to seek
763 unscheduled performance of studies, hospitalization, or treatment by a healthcare
764 professional; may include episodes leading to self-discontinuation of medical therapy
765 by the patient without consulting a healthcare professional.

766 Type 2: any overt, actionable sign of hemorrhage (eg, more bleeding than would be
767 expected for a clinical circumstance, including bleeding found by imaging alone) that
768 does not fit the criteria for type 3, 4, or 5 but does meet at least one of the following

769 criteria: (1) requiring nonsurgical, medical intervention by a healthcare professional,
770 (2) leading to hospitalization or increased level of care, or (3) prompting evaluation.

771 Type 3:

772 Type 3a: Overt bleeding plus hemoglobin drop of 3 to <5 g/dL (provided hemoglobin
773 drop is related to bleed); any transfusion with overt bleeding.

774 Type 3b: Overt bleeding plus hemoglobin drop ≥ 5 g/dL (provided hemoglobin drop is
775 related to bleed); cardiac tamponade; bleeding requiring surgical intervention for
776 control (excluding dental/nasal/skin/hemorrhoid); Bleeding requiring intravenous
777 vasoactive agents.

778 Type 3c: Intracranial hemorrhage (does not include microbleeds or hemorrhagic
779 transformation, does include intraspinal); Subcategories confirmed by autopsy or
780 imaging or lumbar puncture; Intraocular bleed compromising vision.

781 Type 4: CABG-related bleeding: Perioperative intracranial bleeding within 48 h;
782 Reoperation after closure of sternotomy for the purpose of controlling bleeding;
783 Transfusion of ≥ 5 U whole blood or packed red blood cells within a 48-h period;
784 Chest tube output ≥ 2 L within a 24-h period.

785 Type 5: fatal bleeding.

786 Type 5a: Probable fatal bleeding; no autopsy or imaging confirmation but clinically
787 suspicious.

788 Type 5b: Definite fatal bleeding; overt bleeding or autopsy or imaging confirmation.

789

790 **Acquired thrombocytopenia.** Acquired thrombocytopenia is defined as a platelet
791 count decrease by >50% or by $>150 \times 10^9/L$ from baseline.

792

793

794

795

796

797

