225 randomization sequence sealed in an envelope.

226 **5.4 Blinding**

227 Study medications are known by both investigators and subjects. However,
228 independent clinical events committee is blinded to the treatment allocation.

229

230

231

232 Table 1: Study procedure table

| | Baseline | Visit 1 30 days | Visit 2 6 months | Visit 3 12 months |
|--------------------------------------|----------|--------------------|---------------------|----------------------|
| window | | ±7d | ±14d | ±30d |
| Informed consent | X | | | |
| Inclusion/exclusion criteria | X | | | |
| Randomization | X | | | |
| Medical history/demographic features | X | | | |
| Vital signs | X | | | |
| Routine blood and urine test | X | | | |
| Biochemical test | X | | | |
| CK/CKMB and troponin T | X | | | |
| Activated clotting time | X | | | |
| 12- leader electrocardiogram | X | | | |
| Important clinical symptoms | X | X | X | X |
| Clinical evaluation | X | X | X | X |
| Adjunctive medications | X | X | X | X |
| Coronary angiography | X | | | |
| Adverse cardiac events recording | | X | X | X |
| Adverse events recording | | X | X | X |

233 **6. Study population:**

234 **6.1 Target population:**

235 2100 patients who meet the inclusion criteria and receive study medications
236 before coronary angiography.

237 **6.2 Inclusion criteria**

238 (1) Patients aged from 18~80 years, male or female;

239 (2) AMI (STEMI or NSTEMI) patients with planned emergency PCI.

240 ● STEMI within 12 hours after symptom onset or within 12~24 hours with ongoing
241 chest pain, continuous ST segment elevation or new left bundle block.

242 ● NSTEMI within 72 hours after symptom onset.

243 (3) Staged revascularization for non-culprit vessel should be performed after 30 days.

244 (4) Antiplatelet agents (aspirin and clopidogrel, both loading and maintenance dose)
245 are given before PCI per guidelines.

246 (5) Subjects or legal representatives voluntarily participated and signed informed
247 consent, willing to accept study medications and clinical follow-ups.

248 **6.3 Exclusion criteria:**

249 (1) Patients not suitable for PCI; thrombolytic therapy administered before
250 randomization; cardiogenic shock;

251 (2) Any anticoagulant (heparin/LMWH, fondaparinux, warfarin or bivalirudin) or
252 tirofiban administered within 48 hours before randomization;

253 (3) Active or recent major bleeding or bleeding predisposition, including retinal or

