377 ● NACE at 12 months;

378 ● MACCE at 30 days and 12 months;

379 ● Any bleeding events (evaluated by BARC classification) at 30 days and 12
380 months.

381 **8.3 Safety endpoints**

382 ● Stent thrombosis (definite or probable by ARC definition) at 30 days and 12
383 months;

[figure not shown]
- Thrombocytopenia at 30 days;
- Any other abnormal symptoms, signs or laboratory test results with clinical significant.

387

388

389 **9. Study flowchart:**

390 See Figure 1.

391

392

393

394

395

396

Figure 1. Study flowchart

397 **10. AE/SAE reporting**

398

399 There are two classifications of adverse events: adverse event (AE), and serious adverse
400 event (SAE). Adverse events must be monitored until resolved or adequately explained. All
401 serious and unanticipated adverse events must be reported, regardless of the cause. They
402 should be reported to the local IRB/EC and Sponsor within 24 hours of knowledge of the
403 event.

404 **10.1 Definition of AE / SAE**

405 ● **AE**

406 Any adverse medical events occurring in a clinical trial, not necessarily
407 having a causal relationship with the study treatments. Adverse events could be
408 any signs (including abnormal laboratory values), symptom, or temporary disease,
409 whether related or unrelated to the study drug use. An adverse event may be
410 categorized as the following:

- 411 • Mild – signs or symptoms that do not interfere with the patients’ usual
412 activities or is transient and resolves without treatment of sequelae.
- 413 • Moderate – interferes with the patients’ usual activities and/or requires
414 symptomatic treatment.
- 415 • Severe – symptoms causing severe discomfort and significant impact the
416 patient’s usual activities and requires treatment.

417 ● **SAE**

418 A study-related event that is fatal, life-threatening, requires inpatient
419 hospitalization or prolongation of an existing hospitalization, requires
420 intervention to prevent permanent impairment/damage, or results in persistent or
421 significant disability.

422

423 **10.2 Observation and recording of AEs**

424 Investigators should collect and record all AEs occurring from the time of signing
425 informed consent for each subject to end of the follow-up in the clinical study.

426 For AEs, only medical events with clinical worsening compared to baseline are
427 recorded. Abnormal evaluation results at screening or baseline examination are not

428 considered AEs.

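### Table 1 schedules no blood count, cardiac marker or ECG after baseline, so thrombocytopenia, haemoglobin-based BARC 3 grading and Type 4a MI rest on unscheduled tests in an open-label trial

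*Protocol*

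**What the plan says.** Section 5.2 refers the reader to Table 1 for the detailed procedures and allows follow-up visits by telephone or in clinic. Table 1 has four columns: baseline, 30 days, 6 months and 12 months. The blood-test row reads "Routine blood and urine test | X" and the marker row "CK/CKMB and troponin T | X", with later visits blank in both. Biochemistry and the 12-lead ECG are also marked at baseline only. There is no post-procedure or discharge column. The windows are given as "window | | ±7d | ±14d | ±30d".

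The event row reads "Adverse cardiac events recording | | X | X | X", and the adverse-event row has the same pattern, so both are blank at baseline. Section 10.2, in contrast, says "Investigators should collect and record all AEs occurring from the time of signing" consent, and continues to the end of follow-up.

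Section 8.3 makes thrombocytopenia at 30 days a safety endpoint, and section 8.2 makes bleeding by BARC class a secondary endpoint. Appendix 1 gives the definitions. "Acquired thrombocytopenia is defined as a platelet" count decrease of more than 50%, or of more than 150 × 10⁹/L, from baseline. One route to a major bleed is "Type 3a: Overt bleeding plus hemoglobin drop of 3 to <5 g/dL (provided hemoglobin" fall related to the bleed). Type 4a MI needs a troponin rise from a normal baseline, or from elevated values that "are stable or falling. In addition, either (i) symptoms suggestive of myocardial" ischaemia or another listed finding.

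**The concern.** Three outcomes are defined by a change in a laboratory value, and the schedule obtains that value once. A change needs at least two values. If the second is taken only when a clinician sees a reason, the outcome is detected only in patients who were tested.

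Treatment is open-label (section 5.4), so the decision to test is made with knowledge of the arm. The Protocol itself expects an arm difference in the variable at issue: section 3.3.3 reports more platelet decreases with tirofiban plus heparin than with heparin alone. Closer laboratory watching of one arm would raise its detected rate even if the true rates were equal. Blinded adjudication does not repair this, because the committee can judge only values that exist.

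Two smaller matters sit in the same table. Its event rows begin at Visit 1, after the period in which study drug is given. And a Visit 1 held on day 23 leaves the last week of the primary endpoint period without a scheduled contact.

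**Working it through.** **1. Scheduled values against definitions.** Marks after baseline in Table 1, and what each definition in Appendix 1 needs:

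| Outcome | Needs | Scheduled after baseline |
|---|---|---|
| Thrombocytopenia at 30 days | second platelet count | 0 of 2100 patients |
| BARC 3a/3b, haemoglobin route | second haemoglobin | 0 of 2100 |
| Type 4a MI | repeat troponin, and a known trend if baseline is elevated | 0 of 2100 |
| BARC 1, 2, 4, 5; 3a–3c by transfusion, tamponade, surgery, vasoactive agents, or intracranial or intraocular bleeding | clinical record | no scheduled count needed |
| MI types 1, 3, 4b | findings at presentation | no scheduled test needed |

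For thrombocytopenia, if testing is unrelated to the true fall within an arm, detected rate = true rate × fraction with a post-baseline count. The ratio between two arms is then the true ratio multiplied by the ratio of their tested fractions. The Protocol gives no tested fractions, so the bias cannot be sized.

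**2. The plan's own figure.** Section 12.1 states more than 90% power with 700 per arm, 5% loss, two-sided alpha 0.05 and a 45% reduction. Evaluable n = 700 × 0.95 = 665. Power = Φ{[d − 1.96·√(2p̄(1−p̄)/n)] / √[(p₁(1−p₁)+p₂(1−p₂))/n]}.

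- Heparin: p₁ = 0.115, p₂ = 0.115 × 0.55 = 0.06325, d = 0.05175. (0.05175 − 0.03063)/0.01556 = 1.357, power 0.913.
- Heparin plus tirofiban: p₁ = 0.121, p₂ = 0.06655, d = 0.05445. (0.05445 − 0.03133)/0.01592 = 1.452, power 0.927.

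The stated power reproduces and does not depend on this point. As an illustration, if 5% of NACE were missed equally in all arms (an assumed share), power would be 0.897 and 0.913.

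**3. The visit window.** Earliest Visit 1 = 30 − 7 = day 23. Assumptions, none from the Protocol: visits are uniform over days 23 to 37, so half are early and miss 3.5 days on average; 3 to 8% of 30-day events fall in the last week, spread evenly over it; nothing after an early visit is recovered.

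- Share lost = 0.5 × (3.5/7) × 3% to 8% = 0.75% to 2.0%.
- Expected NACE = 700 × (0.115 + 0.121 + 0.06325) = 209.5, about 210.
- Events lost = 210 × 0.0075 to 210 × 0.02 = 1.6 to 4.2.

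The 6-month visit recovers part of this. The Synopsis gives first patient in August 2012 and last patient in December 2013, 17 months, and section 12 runs the primary analysis when all patients have 30 days, about the end of January 2014. With uniform accrual, patients enrolled up to mid or late July 2013 have had the 6-month visit by then: 11.5/17 to 12/17, or 68% to 71%. Applying the loss to the remaining third gives 0.25% to 0.67%, or 0.5 to 1.4 events.

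**4. Event recording.** Table 1 begins at Visit 1; section 10.2 begins at consent. Both cannot describe the same data collection for the index admission.

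**The case against.** The strongest reply is that the Protocol collects events continuously whatever Table 1 shows. Section 10.2 covers all adverse events from consent, section 10.1 counts abnormal laboratory values among them, section 10.3 requires serious events to be reported within 24 hours, and section 14 has the clinical events committee assess bleeding, MI and thrombocytopenia during the trial with access to original data. An X at Visit 1 can be read as covering the interval since baseline. The baseline column includes angiography and the ACT taken after study drug, so it spans the procedure, and an X does not fix a number of samples. Post-PCI blood counts may be usual care.

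Much of this stands, and it rules out stronger readings. A reader might infer that no events are recorded before day 30, or that peri-procedural bleeding is gathered by recall. Sections 10.2, 10.3 and 14 do not support that; what remains is an inconsistency with Table 1. A reader might also infer that bleeding and reinfarction cannot be measured as defined. Most BARC criteria and MI types 1, 3 and 4b need no scheduled test, and the primary endpoint ignores bleeding grade. Nor do the documents show that the Type 4a wording needs a new rule for rising markers: it follows a named universal definition, and section 14 leaves specific endpoint criteria to the committee.

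The reply does not close the laboratory gap. A silent platelet fall produces no adverse event unless someone counts. Usual care across about 82 centres is neither required nor captured by the Protocol, and a column that may hold several samples does not require any.

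**Conclusion.** The point holds for three outcomes: thrombocytopenia at 30 days, the haemoglobin-drop criteria of BARC 3a/3b, and Type 4a MI. Followed as written, the Protocol secures no second value for any of them, and detection may differ by arm because testing is left to unblinded clinicians. Thrombocytopenia is the clearest case, since its definition offers no other route. The size of any bias is unknown; it depends on testing rates that the Protocol does not give.

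The 30-day NACE composite is affected less, through Type 4a MI and not through bleeding grade, and the stated power is unaffected. The conflict between Table 1 and section 10.2 is real and needs reconciling. The early-visit gap is minor: at most about 2 to 4 events in 210 on the assumed timing, and about one or fewer if the 6-month visit recovers the rest. The window is the same in every arm, so no between-arm bias is shown from it. Severity: should-fix.

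**What to change.** 1. Add an in-hospital column (post-procedure and discharge) to Table 1, with a CRF page that records bleeding, ischaemic events and adverse events during the index admission.
2. On that page, capture for every patient the lowest haemoglobin and platelet count, the CK-MB/troponin values and a post-PCI ECG from the index admission, so that ascertainment is the same in all arms.
3. Reconcile the event rows of Table 1 with section 10.2, so that both start at consent.
4. Set the Visit 1 window to day 30 to +7 and count events for the primary endpoint only through day 30.

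The cost is one more CRF page and one Table 1 column. This is mainly data capture if centres already take blood counts after PCI, which is an assumption; where they do not, it adds tests. Some day-30 contacts move up to a week later, which can delay the primary analysis by up to the same amount. No change to the month-12 window is needed for this point.
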